Feelings about Exercise: Protocol

NCT03598647

1/23/19

Background and objectives

Despite the numerous health benefits of regular physical activity (PA), >50% of adults are insufficiently active. Understanding why some individuals choose to engage in PA while others do not is important for informing the development of future PA interventions. Previous research has demonstrated that those who have more positive affective responses to exercise (i.e., the pleasure or displeasure experienced with PA) are more likely to exercise in the future. However, an interesting paradox is that most people generally 'feel good' post-exercise. This begs the questions, if exercise makes people feel good, why don't more people exercise? The answer may lie in one's memory of how exercise makes them feel.

This study seeks to compare exercisers and non-exercisers on their affective responses to exercise, which includes pre-, during, and post-exercise affect, memory of during and post-exercise affect, and anticipated affect towards a future exercise session. It is hypothesized that compared to regular exercisers, non-exercisers will have a more negative memory of how exercise made them feel, and as a result, also have more negative anticipated affect towards a future exercise session. Further, this study seeks to pilot an intervention to improve affective response to exercise among the group of non-exercisers. It is hypothesized that non-exercisers randomized to an affect-based intervention will have a more favorable affective response to exercise following the intervention compared to those randomized to the control intervention (e.g., basic PA recommendations).

Participants

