A total of 59 individuals with overweight/obesity (BMI 25-40 kg/m²), who were weight loss seeking, and between the ages of 18-60 were recruited via self-referral from Internet advertisements. Interested individuals completed a phone screen questionnaire to determine initial eligibility. During this screening, trained research assistants queried potential participants on their moderate-to-vigorous intensity PA (MVPA) over the previous 6 months and a recent 'typical' week. If average MVPA was <30 min/week, the individual was classified as a 'non-exerciser', if average MVPA was ≥150 min/week, the individual was classified as an 'exerciser'. Individuals reporting an intermediate amount of MVPA (30 to <150 min/week) were ineligible for this study as the goal was to target distinctive groups of exercisers vs. non-exercisers. Exclusion criteria included conditions limiting ability to exercise, history of coronary artery disease (i.e., myocardial infarction), stroke, diabetes, pulmonary disease (e.g., COPD), uncontrolled hypertension (i.e., resting BP ≥140/90 mmHg), use of any medication that would affect heart rate (HR; e.g., beta blocker), current enrollment in a weight loss treatment program, history of bariatric surgery, or women who were nursing/pregnant,

Study overview

Individuals deemed eligible based upon the phone screen attended an in-person orientation session in order to learn about the study in greater detail and to provide informed consent in accordance with guidelines set forth by the Internal Review Board of the Miriam Hospital. Upon consenting, participants completed a baseline assessment, which included measures of BMI, fitness, and 1 week of objective physical

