activity (PA) monitoring. Participants then returned to the laboratory for Exercise Session 1, in which they walked on a treadmill for 30 minutes at a moderate intensity. Prior to exercise they reported on anticipated affect (i.e., how they expect the upcoming exercise bout to make them feel), and momentary affect was assessed before, during, and after exercise. In days 1, 3, and 7 following the exercise session, participants were asked to report on their recalled affect via text messaging. They then returned to the laboratory to complete an identical exercise session (Exercise Session 2). Following the completion of the final post-exercise affect measurement, 'non-exercisers' randomly received 1 of 2 PA interventions and then completed additional study measures (described in detail below), while 'exercisers' did not complete any additional study procedures beyond this point.

Baseline Visit: BMI, Fitness Test, Objective PA Measurement: Prior to participating in Exercise Sessions 1 and 2, participants completed the following baseline assessment measures.

BMI. Weight was measured to the nearest 0.1 kg using a calibrated digital scale and height was measured to the nearest 0.1 cm using a wall-mounted stadiometer. Body mass index (BMI) was calculated as kg/m^2 .

Fitness Test. Fitness was measured via a sub-maximal graded exercise test (GXT). Participants walked on the treadmill at 3.0 mph and the speed and incline were increased every three minutes until 75% of age-predicted maximal HR was achieved. Total time spent on the treadmill (in seconds) was used as an indicator of fitness. The purpose of this GXT was to allow participants to gain familiarity with walking on a treadmill and assist in determining the starting treadmill grade for the following exercise visit.

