Assessment of momentary affect. The Feeling Scale (FS; Hardy & Rejeski 1989) was used to assess momentary affect before, during and after exercise. This single-item measure asks participants to rate how they feel 'at the present moment' on an 11-point scale ranging from -5 (very bad) to +5 (very good). *Pre-exercise* affect was assessed as individuals stepped onto the treadmill but before the exercise was started. *During* exercise affect was assessed every 5 minutes during the exercise bout (excluding warm-up), and *post-exercise* affect was assessed immediately after the conclusion of the exercise protocol and exactly 15 minutes later.

Assessment of anticipated affect. Prior to the exercise sessions *anticipated affect* was assessed using a 100mm visual analog scale (VAS). This method for assessing anticipated affect requires participants to denote their response on a continuous line (anchored by 'very bad' and 'very good' similar to the Feeling Scale used for measuring current affect) but does not quantify affect with a numerical response (e.g., "2"), thereby eliminating potential for participants to provide subsequent affect ratings that are simply repetitions of their predictions. Participants were specifically asked "How do you anticipate feeling during exercise?" and "How do you anticipate feeling after exercise?".

Affective Recall and Memory Bias

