In the week following Exercise Session 1, all participants were asked to maintain their typical daily routines of either exercising or not exercising and respond to an online questionnaire assessing their recall of their own affective responses to the exercise session. These questionnaires were completed 1, 3, and 7 days following the exercise session, and participants responded to the questionnaire by clicking on a link provided via text message. In order to avoid direct recall of responses provided on the Feeling Scale, a VAS was used. On days 1, 3, and 7, participants were asked to reflect upon their Exercise Session 1 by responding to following question; "How do you remember feeling overall?" and this was considered an indicator of *global* affective recall. Following this response on day 7 only, participants were asked to further delineate how they remembered feeling during exercise, and post-exercise. Memory bias was assessed by converting VAS recall values to corresponding FS values and then taking the discrepancy between recalled and actual FS values during and post-exercise (e.g., recalled during exercise affect [assessed 7 days post-exercise] minus actual during

exercise affect [average of Feeling Scale scores every 5 minutes during exercise]. A negative number indicates that participants remembered feeling less positive during exercise than they actually felt. Memory bias for post-exercise affect was computed in a similar manner.

Exercise Session 2

In order to collect data on anticipated affect after participants had experienced one laboratory exercise session, all participants were asked to return to the laboratory for a second exercise session at least 1 week following Exercise Session 1. Exercisers were compensated \$50 for participation in the study, while non-exercisers were randomized, and received a brief PA intervention (described below).

Randomized Controlled Trial for Non-Exercisers

Immediately following Exercise Session 2, all non-exercisers were randomized to a brief, affect-based PA intervention (INT; n=15) or an educational PA intervention, which served as the control condition (CON; n=15).

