## **Statistical analysis**

Preliminary analyses were conducted to compare the groups (exercisers vs. non-exercisers) with respect to demographic variables including age, BMI, and gender. Chi Square tests were used to assess between-group differences in categorical variables and independent two-sample t-tests were used for continuous variables. First, unadjusted between-group differences in anticipated affect, pre-exercise affect, and post-exercise affect were assessed using independent two-sample t-tests. Next, using a series of longitudinal linear mixed effects models, we examined between-group (exercisers vs. non-exercisers) differences in serial measures of during-exercise affect (5, 10, 15, 20, 25 minutes) and post-exercise affect (immediate and 15 minutes post-exercise). Models included a subject-specific intercept and adjusted for repeated measures within participant over time. A similar analytic strategy was used to examine group differences in recalled affect (1, 3, and 7 days post-exercise). The goal was to determine the degree to which global recalled affect is associated with (i.e., biased toward) affective responses during or after PA and whether this differs between exercisers and non-exercisers. Correlation analysis was used to examine whether affective recall bias was correlated with anticipated affect towards future exercise. Finally, between-subjects ANOVAs were used to compare non-exercisers receiving the brief cognitive intervention to those in the control group on anticipated affect, affective response to exercise session 3, recalled affect for exercise session 2, and minutes/week spent in MVPA (assessed via the armband). All analyses were carried out in SAS 9.3 with significance level set at .05 a priori. Mixed effects models use a likelihood based approach to estimation, thus making use of all available data without directly imputing missing value.

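### The memory-to-anticipation link is tested only by an unadjusted correlation of a difference score, which alone cannot support or refute it; a regression with recalled and actual affect as separate terms should stand beside it

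*SAP*

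**What the plan says.** The protocol (Background and objectives) expects non-exercisers to have a more negative memory of exercise and, "as a result, also have more negative anticipated affect towards a future exercise session". That is a claim that one variable leads to the other.

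In the SAP's Statistical analysis section, one sentence relates recall to anticipation: "Correlation analysis was used to examine whether affective recall bias was correlated with anticipated affect towards future exercise". It names no covariate. It does not say whether the two groups are pooled, which bias score is used, or which anticipation item it is paired with. The t-tests, mixed models and ANOVAs compare groups or arms on each variable and do not test this link.

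The protocol (Affective Recall and Memory Bias) defines bias by "taking the discrepancy between recalled and actual FS values during and post-exercise", using the day-7 recall. There are two scores, since "Memory bias for post-exercise affect was computed in a similar manner". Anticipation also has two items, one of which is "How do you anticipate feeling during exercise"; the other asks about feeling afterwards.

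The variables needed for adjustment are already collected. Group is fixed by design, because "the goal was to target distinctive groups of exercisers vs. non-exercisers" (Participants). Anticipation was measured before Session 1: "Prior to exercise they reported on anticipated affect (i.e., how they expect the upcoming exercise bout to make them feel" (Study overview). Actual affect is the Feeling Scale record from Session 1.

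**The concern.** Three features can separate this correlation from the memory effect that the hypothesis describes.

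- **Actual affect sits inside the bias score with a minus sign.** If a better session also raises later anticipation, the correlation is pushed downward. A real recall effect can then be hidden, or a negative correlation can appear where recall has no effect.
- **Group.** If the groups are pooled and differ on both variables, as the hypothesis expects, group alone can produce a positive correlation.
- **Prior expectation.** Expectation held before Session 1 may colour recall, actual affect and later anticipation. Its net effect on a difference score can be nil, positive or negative.

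At stake is the mechanistic conclusion. A significant correlation could be read as support for worse memory leading to worse anticipation, and a null or negative one as evidence against it. Neither reading is safe from this statistic alone.

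**Working it through.** **Inputs.** n = 59 (Protocol, Participants). Non-exercisers: 15 + 15 = 30 (Randomized Controlled Trial for Non-Exercisers). Exercisers: 59 − 30 = 29, if every non-exerciser was randomised. Alpha .05 (SAP), taken as two-sided. The documents give no expected correlation, SD, group difference or power, so there is no planned figure to reproduce. Every effect size below is assumed and in SD units. Rejection rates come from simulation with normal data. The full regression adjusts for actual affect, group and Session 1 anticipation.

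**1. What n = 59 can detect.** Critical |r| = t/√(57 + t²) = 0.256. The r detectable with 80% power is tanh[(1.960 + 0.842)/√56] = 0.358.

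**2. The difference score.** Let R be recalled affect, A actual affect and T later anticipation, all with unit SD, corr(R, A) = ρ, and T = βR + γA + error. Then

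- cov(R − A, T) = β(1 − ρ) − γ(1 − ρ) = (β − γ)(1 − ρ)
- var(R − A) = 2(1 − ρ)
- corr(R − A, T) = (β − γ)·√[(1 − ρ)/2]

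With ρ = 0.6 the multiplier is √0.2 = 0.447.

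| Recall effect β | Actual-affect effect γ | Expected r | Correlation significant | Full regression significant |
|---|---|---|---|---|
| 0.3 | 0 | 0.134 | 17% | 44% |
| 0.4 | 0 | 0.179 | 27% | 71% |
| 0.5 | 0 | 0.224 | 40% | 91% |
| 0.4 | 0.3 | 0.045 | about 6% | 84% |
| 0 | 0.3 (prior anticipation 0.5) | −0.134 | 17%, nearly all negative | 5% |

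When β = γ the expected r is 0 whatever ρ is. At 0.3 or 0.4 each, with ρ from 0.5 to 0.7, the correlation is significant in about 5% of runs and the regression in 46% to 92%. For β = 0.4 and γ = 0, the comparison is 39% against 82% at ρ = 0.4, and 16% against 47.5% at ρ = 0.8.

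Adjusting the bias score for group and Session 1 anticipation alone does not cure this. With γ = 0.3 and no recall effect, that model still rejects in 20.6% to 23.5% of runs, nearly all negative.

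**3. Group, if pooled.** With a difference of d SD on both variables and no other link, r = pq·d²/(1 + pq·d²), where pq = (30/59)(29/59) = 0.25. For d = 0.5, 0.8 and 1.0, r = 0.059, 0.138 and 0.200. Rejection is 7.5%, 18% and 34% (5% at d = 0.3). A by-group analysis removes this.

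**4. Prior expectation** (path 0.5 to later anticipation, no recall effect). Rejection is 5% if expectation moves actual and recalled affect alike, and 8%, mostly negative, if it acts only through actual affect. If it moves recall only, by 0.2, 0.3 or 0.4, rejection is 14%, 25% or 40%.

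**5. Limits of the full regression.**
- If bias itself drives anticipation and the covariates do not predict it, power falls from 79% to 67–68% at slope 0.35, and from 64% to 53% at slope 0.30. If prior anticipation also correlates 0.4 with bias, it falls to 58% and 45%.
- If actual affect (0.3) and prior anticipation (0.5) do predict later anticipation, power rises from 38% to 81% and from 25% to 67%.
- With γ = 0.3, no recall effect, and reliability 0.8 for Session 1 anticipation and 0.9 for actual affect, it rejects in 5% to 8% of runs. With 0.8 for both, 7% to 11%.
- Suppose an unmeasured disposition loads 0.5 on Session 1 anticipation, 0.3 on actual affect, an extra 0.2 or 0.3 on recall, and 0.4 or 0.5 on later anticipation, with no memory effect. The regression rejects in 9% or 17–19% of runs, the simple correlation in 6% or 12–13.5%.

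**The case against.** The strongest reply is that the SAP asks only whether two variables are correlated, and a correlation answers that. The causal wording is in the protocol's hypothesis. This stands: the planned analysis is not invalid. The remaining difficulty is that no other planned analysis relates recall to anticipation, so this result is likely to carry the hypothesis.

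A second reply is that once actual affect is in the model, the bias slope equals the recall slope, so the regression changes the question. A more negative memory can mean a lower recalled level or a larger discrepancy. This also stands. A reader might infer that the adjusted model must replace the correlation as the main analysis, but that is partly a choice of estimand, and the documents do not settle it.

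Third, the 5% rejection rate of the full regression holds because it adjusts for exactly the variables that generated the data. With an unmeasured disposition it can do worse than the simple correlation, because subtracting actual affect removes some shared disposition. A reader should not infer that adjustment removes confounding. Nor does the regression estimate an indirect effect from group through memory to anticipation.

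Fourth, the inputs are weakly anchored. The protocol's statement about "those who have more positive affective responses to exercise" concerns later exercise behaviour, so it makes an effect of actual affect on anticipation plausible without establishing it. The SAP does not say that the groups are pooled, so group confounding cannot be taken as fact.

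Finally, the randomised arms are compared on anticipated affect after an intervention aimed at recall, which bears on the mechanism. With 15 against 15 and several components, it is indirect evidence and does not replace a test of the link.

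**Conclusion.** The point holds as one of interpretation and reporting. The bias correlation is a sound marginal association but a poor sole basis for a conclusion about memory and anticipation. The core of this is algebraic: with equal SDs it measures recall effect minus actual-affect effect, whether analysed pooled or by group. The sizes are conditional on the assumed effects. The group artefact is small up to about 0.5 SD and absent by group, and prior expectation can distort the result in either direction by an unknown amount. The documents do not support a stronger conclusion that the planned correlation is wrong, that it is certainly biased, or that the randomised comparison is compromised.

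**What to change.** Keep the planned correlation and state whether it is pooled or by group. Beside it, report a linear regression of Session 2 anticipated affect on day-7 recalled affect and actual Session 1 affect as separate terms, adjusted for group. Fit it with and without the same item's Session 1 anticipated affect. Including that term limits the question to memory of Session 1; omitting it allows for earlier memories that Session 1 anticipation may already reflect.

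Pair the during-exercise scores with the 'during' item and the post-exercise scores with the 'after' item. Report slopes with 95% confidence intervals. Label the regression post hoc if the data have already been analysed, which the SAP's past tense suggests. Call every result an association, and draw no conclusion for or against the hypothesised memory effect from the bias correlation alone.

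The cost is SAP wording and 2 items × 2 models = 4 regressions on data already collected. Relative to the simple correlation, the larger model uses three more degrees of freedom. The report should acknowledge the possible loss of power if bias itself is the driver (about 79% to 67% at slope 0.35), and the residual confounding from measurement error or unmeasured disposition.

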Objective PA Measurement. While participants were deemed eligible for this study based upon self-report measures of PA, direct PA monitoring was also performed to confirm that 'exercisers' and 'non-exercisers' significantly differed on MVPA. All participants wore a previously validated activity monitor (Sensewear Armband, Body Media Inc., Pittsburgh PA) for 1 week and were asked not to alter their activity levels during this period. The monitor is worn on the upper arm and assesses movement and energy expenditure, however the device does not provide any information or feedback to participants. Minute-by-minute data were collected, and using proprietary algorithms, MET values were computed for each minute the device was worn. Exercise groups were compared on time spent engaging in bout-related MVPA (≥ 3 METs, ≥ 10 min).

Exercise Session 1

Exercise Protocol. Following completion of all assessment measures, participants returned to the laboratory for Exercise Session 1. Upon arrival, participants were given a detailed description of the upcoming exercise protocol and were equipped with a HR monitor. Immediately prior to the start of the exercise bout, participants were asked to report their pre-exercise *momentary* affect using the Feeling Scale and their *anticipated*

affect towards the upcoming exercise bout using a visual analogue scale (see below for additional detail on affect measures). They then completed the exercise protocol which consisted of a 2-minute warm-up, followed by 30 minutes of moderate-intensity walking (70-75% of age-predicted maximal HR), and a 2-minute cool-down. This exercise duration and intensity was chosen because it is consistent with the American College of Sports Medicine's exercise guidelines, and is feasible for individuals with overweight/obesity. Starting exercise intensity was estimated using HR data from the baseline fitness test. Heart rate was monitored every minute and the treadmill grade or speed was adjusted by trained research staff if the subject's HR fell outside the target range for two consecutive minutes. Affect was assessed every 5 minutes during exercise, immediately post-exercise, and 15 minutes following the completion of the exercise bout.

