exercise session (e.g., improved mood, feeling energized, feeling accomplished/proud, or feeling good about doing something beneficial for the body). They then shared their responses with the interventionist and participants were encouraged to think about these positive experiences, feelings, and motivations for engaging in exercise often, and specifically during the next exercise session.

Post-intervention assessment

Non-exercisers in both arms were informed they could increase their PA following Exercise Session 2 if they desired, and they were given the Sensewear armband to wear for 1 week to objectively assess whether there was an intervention effect on bout-related MVPA. Further, during the week following Exercise Session 2, all non-exercisers were asked to complete recalled affect questionnaires for Exercise Session 2 at 1, 3, and 7 days following the session, as was done previously.

Exercise Session 3

One to two weeks following Exercise Session 2, non-exercisers from both the control and intervention groups returned to the laboratory for a third exercise session (Exercise Session 3). This session was identical to the previous exercise sessions and measures of anticipated affect, pre-, during, and post-exercise affect were obtained. All non-exercisers attending Exercise Session 3 (INT and CON) were compensated \$50 for their time.

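### The only randomised comparison (15 per arm) is analysed without a baseline term, although an earlier value of each outcome measure was on record before randomisation; precision is lost if its correlation with the outcome exceeds about 0.2.

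*SAP*

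**What the plan says.** The SAP (Statistical analysis) describes the comparison of the two randomised arms in one sentence: "between-subjects ANOVAs were used to compare non-exercisers receiving the brief cognitive intervention to those in the control group on anticipated affect", on affective response to Session 3, on recalled affect for Session 2 and on weekly MVPA from the armband. No covariate, change score or repeated-measures term is named. The mixed models earlier in that section are described for exercisers against non-exercisers.

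The Protocol fixes the timing. Under Randomized Controlled Trial for Non-Exercisers: "Immediately following Exercise Session 2, all non-exercisers were randomized to a brief, affect-based PA intervention (INT; n=15", with 15 in the control arm as well. Study overview places the intervention later than the last Session 2 rating: "Following the completion of the final post-exercise affect measurement".

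The Protocol also shows what was on record by then:

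- **Anticipated affect and Feeling Scale affect:** taken at Session 1 and again at Session 2, an identical session. The purpose given for Session 2 is "In order to collect data on anticipated affect after participants had experienced one laboratory exercise session".
- **Recalled affect:** for Session 1, "These questionnaires were completed 1, 3, and 7 days following the exercise session" (Affective Recall and Memory Bias).
- **MVPA:** "All participants wore a previously validated activity monitor" for a week at baseline (Objective PA Measurement).

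On Session 3, the follow-up session, the Protocol says: "This session was identical to the previous exercise sessions and measures of anticipated affect, pre-, during, and post-exercise affect were obtained".

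**The concern.** This is the trial's only randomised comparison and its test of the intervention hypothesis. With 30 people, much of the spread in a later affect rating may be stable differences between people that the earlier ratings already capture. An ANOVA on follow-up values alone leaves that spread in the error term. It also leaves any chance baseline difference between arms in the estimate, shifting it by roughly the correlation times the imbalance.

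At stake are the width of the confidence intervals and the chance of detecting a real effect. Validity is not at stake: after randomisation the unadjusted comparison is unbiased on average, with the nominal error rate.

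**Working it through.** The plan gives no power, effect size, SD or correlation, so there is no figure of its own to reproduce.

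**Inputs from the documents.** 15 per arm (Protocol, Randomized Controlled Trial for Non-Exercisers); significance level 0.05 (SAP).

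**Assumptions.** Two-sided test; 30 complete cases; normal data with a common slope; true effect 0.8 SD; correlation *r* between covariate and outcome within arms from 0 to 0.7.

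**Step 1: variance.**

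- ANOVA: Var = 2/15 = 0.133 in SD² units, so SE = 0.365 SD, on 28 df.
- ANCOVA with one covariate: Var = (2/15)(1 − r²)(1 + 1/26), on 27 df. The factor 1 + 1/26 = 1.038 is the price of estimating the slope.
- At r = 0.5 the ratio to ANOVA is 0.75 × 1.038 = 0.779, equivalent to 15/0.779 = 19.3 per arm under ANOVA.

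**Step 2: break-even.** Setting (1 − r²)(27/26) = 1 gives r = √(1/27) = 0.19. Allowing for the lost degree of freedom in the 95% confidence interval gives 0.20.

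**Step 3: power and detectable effect** (noncentral t; noncentrality 0.8/SE). For ANOVA, 0.8/0.365 = 2.19.

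| Analysis | Variance ratio | Power at 0.8 SD | Effect detectable with 80% power | Equivalent ANOVA size per arm |
|---|---|---|---|---|
| ANOVA | 1 | 56.2% | 1.06 SD | 15.0 |
| ANCOVA, r = 0 | 1.038 | 54.5% | 1.08 SD | 14.4 |
| ANCOVA, r = 0.2 | 0.997 | 56.2% | 1.06 SD | 15.0 |
| ANCOVA, r = 0.3 | 0.945 | 58.4% | 1.03 SD | 15.9 |
| ANCOVA, r = 0.5 | 0.779 | 66.8% | 0.94 SD | 19.3 |
| ANCOVA, r = 0.7 | 0.530 | 82.7% | 0.77 SD | 28.3 |

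Simulation reproduced the variance ratios and the powers.

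**Step 4: two covariates.** The factor becomes 1 + 2/25 = 1.08, on 26 df. Power is 52.8%, 56.7%, 64.9% and 81.1% at a multiple correlation R of 0, 0.3, 0.5 and 0.7. Break-even is R = 0.28.

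**Step 5: chance imbalance.** The baseline difference between arms also has SD √(2/15) = 0.365 SD, so P(|difference| > 0.5 SD) = 0.17 for each covariate. Among simulated trials with such an imbalance and no true effect, ANOVA rejects in about 7%, 11 to 12% and 18% at r = 0.3, 0.5 and 0.7; ANCOVA rejects in about 5% throughout. The mean shift of the ANOVA estimate in those trials is 0.20, 0.33 and 0.47 SD.

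**Step 6: change scores.** Their variance ratio is 2(1 − r). Power is 43%, 56% and 78% at r = 0.3, 0.5 and 0.7: below ANCOVA at each, and below the plain ANOVA at r = 0.3.

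**The case against.** The strongest reply is that the plan contains no error. ANOVA after randomisation is valid, this part of the study is labelled a pilot, and the documents set no power target. The gain rests on an unknown correlation; at r = 0.3 it is only 58.4 − 56.2 = 2.2 points. This stands, and it is why the point concerns efficiency and is shown as a range. The pilot label does not remove it, since imprecision is the main weakness of a 30-person comparison.

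The raised false-positive rates in Step 5 apply only to the 17% of trials with a large imbalance. Because the overall rate is 5%, the other 83% must average (0.05 − 0.171 × rate)/0.829, which is about 4.5%, 3.6% and 2.4% at r = 0.3, 0.5 and 0.7. That is correct. The documents report no actual imbalance between the arms.

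Recall of Session 2 is itself collected after randomisation. Its candidate covariates are recall of Session 1 (same scale, different session) and experienced Session 2 affect (same session, different scale). That qualification stands; both were recorded beforehand.

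MVPA is the weakest case. Participants were selected on self-reported MVPA below 30 minutes a week. They were asked not to change their activity in the baseline week but told that they could increase it in the later one. The correlation may be low, and the normal-theory figures may not carry over if values cluster near zero.

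Finally, the SAP is in the past tense, so covariates would be chosen after the fact, and ANCOVA drops anyone whose covariate is missing. Both are fair; they shape the fix without removing the case for it.

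**Conclusion.** The concern holds. The randomised comparison ignores relevant measurements that the study already had, and adjustment pays once the correlation exceeds about 0.2. For an assumed 0.8 SD effect, the outcome ranges from a loss of 1.7 points of power at r = 0 (56.2 − 54.5) to a gain of 10.6 at r = 0.5 (66.8 − 56.2) and 26.5 at r = 0.7 (82.7 − 56.2).

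A correlation above 0.2 is plausible for the affect ratings, which repeat the same scales in the same people at identical sessions, but the documents do not give it. For MVPA the benefit is uncertain. With fewer completers the break-even on interval width rises only to 0.23 at 12 per arm and 0.26 at 10 per arm.

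This should be changed, as a matter of precision. It does not make the planned analysis invalid.

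**What to change.** Replace the ANOVAs with ANCOVA, or with a mixed model that has the pre-randomisation value as covariate. Do not use change scores.

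1. **Session 3 anticipated affect:** adjust for the Session 2 value, which, like the outcome, reflects anticipation after laboratory experience.
2. **Session 3 Feeling Scale affect:** adjust for the mean of the matching Session 1 and Session 2 values, entered as one covariate.
3. **Recall of Session 2:** adjust for experienced Session 2 Feeling Scale affect. Add recall of Session 1 only if the second degree of freedom is accepted.
4. **MVPA:** adjust for baseline-week armband MVPA.

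Report the unadjusted ANOVA beside each adjusted result, and state that the covariates were chosen after the fact. Give the observed correlations and the number of participants with a missing covariate. Optionally, extend the SAP's existing mixed-model approach to the serial recall and Feeling Scale outcomes in this comparison, so that all available values are used.

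The cost is one of 28 degrees of freedom per outcome (two for recall if both covariates enter). If the covariates turn out unrelated to the outcome, that is at most about 2 points of power with one covariate, or 56.2 − 52.8 = 3.4 with two. It is a re-analysis of existing data.
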